**Form A**

IRB #	STU 2022-0306
--------------	----------------------

**Form A**

IRB #

STU 2022-0306

**PROTOCOL FORM / RESEARCH  
DESCRIPTION**

If an item does not apply to your research project, indicate that the question is "**not applicable**" – do not leave sections blank

**Click once on the highlighted entry in each box to provide your response.** Click the item number/letter or word, if hyperlinked, for detailed instructions for that question. If your response requires inserting a table, picture, etc, you may need to first delete the box that surrounds the answer and then insert your table or other special document.

**1. Purpose and objectives.** *List the purpose and objectives:*

Title: Exploration of Central Venous Catheter Protective Devices in the Pediatric Population: A Mixed Methods Study

CVCs have multiple uses, including medication delivery (Government of Alberta., 2020) and provision of Total Parental Nutrition (TPN). While the CVC is necessary for the patient's treatment, it is not without risk. Patients with CVCs may experience catheter breaks, dislodgement, or central-line associated bloodstream infections (CLABSI). As a result, patients experience increased health care utilization, possible restriction of movement, and delayed development. The CDC established guidelines to prevent CLABSI in hospitalized pediatric patients that include keeping the catheter clean, dry, and intact (CDC, 2015). A paucity of literature supports nursing practice for preventing contamination, catheter dislodgement, and catheter breaks (Chamblee et al., 2020; Langford et al., 2021). One promising intervention is a wearable device (Gus Gear Vest) that can keep the catheter secure while protecting it from contamination and other risks.

Gap: There is a lack of research that focuses on wearable devices in pediatric patients.

The primary purpose of this study is to explore caregiver and nurse satisfaction of pediatric patients with CVCs that utilize a wearable protective device.

The specific aims of this study are to:

- 1) to determine the feasibility of utilizing a wearable device
- 2) to prospectively measure and evaluate parent and nurse satisfaction with the protective wearable device.

## Form A

IRB #

STU 2022-0306

### 2. Background.

- Describe past experimental and/or clinical findings leading to the formulation of your study.
- For research involving investigational drugs, describe the previously conducted animal and human studies.
- For research that involves FDA approved drugs or devices, describe the FDA approved uses of this drug/device in relation to your protocol.
- Attach a copy of the approved labeling as a product package insert or from the Physician's Desk Reference.

You may reference sponsor's full protocol or grant application (section number and/or title) or if none, ensure background includes references.

Please respond to all components of this item, or clearly indicate which components are not applicable.

#### a. Background

Previous studies have found that CVC complications and failure are recognized problems experienced by patients (Ullman et al., 2015b). One in four CVCs fail before completing intended therapy in the pediatric population (Ullman et al, 2015a). Mechanical complications may include catheter breaks and catheter dislodgement which may delay recovery or interrupt treatment (Cesaro et al., 2004). Mechanical complications are a common cause for repair, especially in the pediatric population, due to the child's lack of safety awareness, nearly constant movement, and poor impulse control (Cesaro et al., 2004). In 2020, 21,399 CLABSI's were reported by CDC (n.d.b). CVC complications lead to a significant burden on the patient and the healthcare system including additional time in the hospital, lost time receiving treatment, loss of access sites, and the potential for further complications including death (Peng et al., 2011; Ullman et al., 2015a). Additionally, there is a 3-fold increase in sepsis in the 30 days following line repair (Lungdren et al., 2012). There is a lack of research that focuses on preventing contamination of CVCs by bodily fluids, food/ liquids, and other contaminants outside of the traditional securement devices. CVC usage may impact the patient's quality of life (Tremolada et al., 2005). Parents of leukemia patients reported a higher quality of life when retaining prior activities or routines (Tremolada et al., 2005). However, there is a lack of research studies that focus on devices that promote normal levels of activities and routines in pediatric patients with CVCs while still maintaining the safety of the CVC.

Preventing CVC trauma impacts long-term outcomes by preserving central access. This is an essential task of registered nurses. Traditional securement devices are occlusive, adhesive, and transparent dressings covering the CVC entry point (Barnes et al., 2015; Bogart, 2015; Ista et al., 2016). In the United States, the CDC (n.d.a) and CDC (2015) provide guidelines and recommendations for managing and caring for pediatric patients with CVCs while in the hospital. Registered nurses are the primary role responsible for managing and accessing CVCs in hospitals and outpatient settings. There are many methodologies for mitigating CLABSI's, such as keeping an occlusive, transparent dressing clean, dry, and intact, as well as specific times to change the dressing, tubing, and other mechanisms needed to provide treatment and manage the CVC

**Form A****IRB #****STU 2022-0306**

(Barnes et al., 2015; CDC, 2015).

Maintaining a clean and dry transparent dressing is challenging for active, mobile pediatric patients. Nurses are aware of the many risks associated with CVC care and need to invest in new options to keep their patients safe. Nursing practices surrounding CVC care continue to change as new evidence regarding management evolves (Jarding & Makic, 2021). Patients and families have designed wearable devices to mitigate CVC risk factors and promote normal growth and development (Gus Gear, n.d.). The CVC protective wearable device assists in protecting the CVC without interfering with the child's mobility (Gus Gear, n.d.). Therefore, nurses are interested in evaluating parents' and nurses' satisfaction of pediatric patients with CVCs that utilize a wearable protective device.

**Form A**

**IRB #**

**STU 2022-0306**

**b. Current practice**

Once a patient receives a CVC they are dressed with an occlusive, adhesive, transparent dressing, and a chlorhexidine impregnated sponge unless chlorhexidine is contraindicated for the patient. Standard of care in the hospital setting is to change the dressing every 7 days or when soiled or no longer occlusive. The standard of care and implications for changing the dressing will not be altered with this study.

**Form A**

IRB #

STU 2022-0306

**3. Study Design.**

Describe the study design (e.g., single/double blind, parallel, crossover, etc.) Consider inserting a scheme to visually present the study design.

This is a sequential, convergent mixed methods study design in which qualitative interview data will be collected first followed by quantitative data.

**Scheme and Outcomes:** Identify eligible patients--Informed Consent--Provide education and two protective wearable device--Demographic data (electronic health record)--Interview parent on device--Every month complete 30-day satisfaction survey for a total of three data collection period-Discharge from study.

**Nurse data collection scheme:** Study participants hospitalized at time of enrollment in study or anytime during the study period. Nurse of patients using device will complete satisfaction survey.

1. Feasibility measurement from Parents of Children using the Gus gear vest device

Interview parents (of children using Gus gear vest) on device.

[Time Frame: Two weeks from recruitment, plus or minus seven days.]

2. Satisfaction survey from Parents of Children using the Gus gear vest device

Every month complete 30-day satisfaction survey for a total of three data collection period

[Time Frame: Every month for a total of three data collection periods up to 3 months. Team will have plus or minus seven-day timeframe around the 30-day window to collect the data.]

3. Satisfaction survey from nurses

Satisfaction survey from nurses of Children using the Gus gear vest device

[Time Frame: Anytime during the study period up to nine months.]

**4. Research Plan / Description of the Research Methods:****4.a. Provide a comprehensive narrative describing the research methods.**

- 1) Provide the **order in which tests/procedures will be performed**,
- 2) Provide the **setting** for these events and a description of the **methods used to protect privacy** during the study.
- 3) Provide the **plan for data analysis** (include as applicable the **sample size calculation**)

Please respond to all components of this item, or clearly indicate which components are not applicable.

## Form A

IRB # STU 2022-0306

The PI and Co-PIs will provide training to the research team to promote consistency in data collection. Study team personnel will approach eligible patients for consent. Once consented, patients/ parents will be provided two protective wearable devices. Education on how to wear the protective wearable device will be provided. Demographic data will be captured utilizing chart review.

An interview with the parent on the device will be obtained at enrollment to the study. Interviews will be audio-recorded and transcribed verbatim using the TranscribeMe Application. Qualitative analysis will require thematic saturation which typically requires at least 8 interviews (Namey et al., 2016). Parents will be interviewed using the feasibility interview guide. Interviews will be open-ended questions lasting 15 to 45 minutes long utilizing an interview guide for consistency of interviewing probes may be utilized such as, "Can you tell me more about that?"

Parents will be requested to complete 30-day satisfaction survey every month for a total of three data collection period. Sampling will continue for up to 30 patients to meet minimum requirements for statistical analysis for feasibility and satisfaction data.

**Nurse data collection scheme:** If the patient is hospitalized, the nurse caring for the patient will be asked to complete the nurse satisfaction survey. Study participants hospitalized at time of enrollment in study or anytime during the study period.

**Setting:** The study will be conducted at a large, tertiary pediatric healthcare system on the primary Dallas campus. Primary targeted patients are within the inpatient and ambulatory settings for patient specialties: 1) gastroenterology, 2) transplant, and 3) pulmonary.

The gastroenterology floor has approximately 1124 admissions per year with about 40 TPN dependent patients that require external CVCs for treatment. Gastroenterology diagnosis that are seen include short gut syndrome, microcolon-intestinal hypoperistalsis syndrome. The gastroenterology population is also seen in the ambulatory setting with approximately 14,000 visits per year. Patients with central venous catheters admitted to inpatient oncology, transplant, pulmonary, general pediatrics, and rehabilitative floors will be considered as identified by the central line associated bloodstream infection committee or infectious disease to be approached by the study team.

### Inclusion Criteria:

- Patients with CVCs ages 0 to 12 years of age
- May currently utilizing or historically utilized the interventional wearable protective device
- Caregiver or parent available
- English and Spanish speaking subjects

### Exclusion Criteria:

- Females with Tanner 2 breast or greater breast development. Justification: the wearable device will not fit properly to secure the CVC and may increase the risk of complications. If the patient does develop breast during the time of the study, then the patient will no longer wear the wrap and will go back to securing their device in the traditional way. Tanner 2 breast development will be evaluated in the screening process of patients.
- Patients in critical care services such as neonates, trauma/ neurology intensive care unit, or cardiac intensive care unit. Justification: These patients are not mobile with their CVC and not the targeted population.

Screening for eligibility will take each morning through review of the inpatient and ambulatory patient census. Patients charts will be reviewed to determine if they meet inclusion criteria. Once an eligible patient is identified, an individual from the study team will approach the family and introduce the study. If the family is interested in the study, an individual from the research team will consent the family and measure the patient for the wearable device. The caregiver and nurse will have the opportunity to simulate placement of the wearable device on a manikin. Two wearable devices will be provided to the patient/ caregiver. Together the caretaker and study team personnel will fit the protective wearable device on the patient.

Study personnel will collect study participant demographic data from the electronic health record using the demographic form. Caregivers will be interviewed using the feasibility interview guide. Interviews will be audio-recorded and transcribed verbatim using the TranscribeMe Application. Qualitative analysis requires thematic saturation or no new themes emerging in the

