### Data Analysis:

Descriptive statistics will be used to describe the sample population, total satisfaction scores, and feasibility and fidelity of the protective device. Frequencies of nurse and caregiver reporting completion of the patient wearing the protective device will be calculated to evaluate feasibility and fidelity. Nurse satisfaction scores will be analyzed using a one sample t-test and descriptive statistics. Parent satisfaction scores will be analyzed using repeated measures ANOVA and descriptive statistics.

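### Feasibility (Aim 1) is measured only in families who consent, and no uptake or refusal record is planned, so the result may not carry over to eligible families

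*Combined protocol and SAP*

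**What the plan says.** Form A, section 1, sets the first aim as "to determine the feasibility of utilizing a wearable device". It states no threshold, target rate or denominator.

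Section 3 names the first outcome as "Feasibility measurement from Parents of Children using the Gus gear vest device". This is a parent interview. In section 4.a, the quantitative Data Analysis adds that "Frequencies of nurse and caregiver reporting completion of the patient wearing the protective device will be calculated to evaluate feasibility and fidelity". The monthly parent surveys also collect feasibility.

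The recruitment steps follow the exclusion criteria in section 4.a:

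- Candidates are found from daily lists: "Screening for eligibility will take each morning through review of the inpatient and ambulatory patient census".
- Contact with families comes next: "Once an eligible patient is identified, an individual from the study team will approach the family and introduce the study".
- Only those who show interest go on to consent and are measured for a vest.

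Devices come after that: "Once consented, patients/ parents will be provided two protective wearable devices". The Setting paragraph adds a second route. On several other inpatient floors, patients are put forward by the bloodstream infection committee or by infectious disease. The inclusion criteria allow current and past users of the vest. Enrolment is capped at 30 patients.

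Neither the recruitment text nor either Data Analysis section describes a screening or refusal log, reasons for declining, or an uptake outcome.

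**The concern.** Whether families take up the vest when it is offered, and whether children keep wearing it, are both parts of feasibility. The plan measures the second part, and only in families who have already agreed. A parent who declines because the child would not tolerate a vest is informative about Aim 1, and under this plan that information is lost. The loss occurs before enrolment, so careful follow-up of enrolled families cannot recover it.

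What is at stake is how far the conclusion reaches. A report of high wear and good satisfaction would read the same whether nearly all approached families joined or only half did. Aim 1 is worded without restriction, so readers would tend to apply the result to eligible children in general.

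**Working it through.** **The plan's own figure.** The only number is the cap of 30 patients. It cannot be reproduced, because no precision target, rate, effect size, SD, alpha or power is given.

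**Where each feasibility measure starts.**

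| Measure | Source | Before or after consent |
|---|---|---|
| Parent interview | Parents of children using the vest | After |
| Monthly survey | Enrolled parents | After |
| Reported wearing | Caregivers and nurses of enrolled children | After |
| Uptake, refusals, reasons | Not planned | – |

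**Size of the possible gap.** Let N be the number of families approached to enrol 30, and let 27 of the 30 enrolled children wear the vest. Both N and 27 are assumptions.

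- Uptake = 30/N.
- Wear among enrolled = 27/30 = 90% (exact 95% CI 73.5 to 97.9).
- If every decliner is a non-user, wear among approached = (30/N) × (27/30) = 27/N. This is a lower bound.
- Largest gap = 27/30 − 27/N.

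| Assumed acceptance | N | Declined | Uptake (exact 95% CI) | Lower bound 27/N (exact 95% CI) | Largest gap |
|---|---|---|---|---|---|
| 100% | 30 | 0 | 100% | 90% (73.5 to 97.9) | 0 points |
| about 90% | 34 | 4 | 88% (72.5 to 96.7) | 79% (62.1 to 91.3) | 10.6 points |
| 75% | 40 | 10 | 75% (58.8 to 87.3) | 68% (50.9 to 81.4) | 22.5 points |
| 50% | 60 | 30 | 50% (36.8 to 63.2) | 45% (32.1 to 58.4) | 45 points |

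**If only some refusals concern the vest.** Suppose half the decliners refuse because of the vest, and the rest are left out of the denominator. The figures become 27/(30 + 2) = 84%, 27/(30 + 5) = 77% and 27/(30 + 15) = 60% for N = 34, 40 and 60. If decliners would wear the vest as often as enrolled children do, the gap is zero at any N.

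The gap thus depends on how many families decline and why. The plan records neither.

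**The case against.** The strongest reply is that the plan declares its population openly. The outcome concerns children using the vest, and wear frequency is paired with fidelity ("feasibility and fidelity of the protective device"). If feasibility means workable use among families who have the device, consenting families are the right denominator and the measure is not in error. The study is also small and exploratory, with no comparator, threshold or go/no-go rule, so no planned test or decision changes. This stands as far as it goes: the issue is scope of inference. But Aim 1 is not limited to consenting families, and uptake is what would tell a reader whom the result covers.

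Four stronger readings are tempting, and the documents do not support them.

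- A reader might infer that daily screening already identifies the decliners. It identifies eligible patients. A refusal can appear only at the approach, and nothing says it is recorded.
- A reader might infer that every eligible family is approached. On some floors the approach seems to depend on referral, so consented over approached is not clearly uptake in the whole eligible population.
- A reader might take 27/N as the true rate of wear. Families are introduced to a study with a recorded interview, repeated surveys and chart audit. Declining that is not declining a vest, and a current user who declines the study may still be wearing one.
- A reader might infer that admitting prior users tilts the sample towards vest supporters. Past users include families who stopped, so the direction is not established.

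**Conclusion.** The point holds as a limit on what Aim 1 can conclude. Feasibility is estimated only among consenting families and their nurses, and no uptake or refusal information is planned, although the team meets families in person. The result may overstate feasibility in the eligible population.

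A reader might go further and say that feasibility is overstated. The documents do not show this, because they give no acceptance rate. With 27 of 30 enrolled children assumed to wear the vest, the shortfall among approached families is at most about 11, 22.5 or 45 points at about 90%, 75% or 50% acceptance. It is zero if nobody declines. These figures rest on the assumed wear and acceptance rates and on counting every decliner as a non-user.

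The change is worth making before recruitment starts, because refusals and their reasons cannot be reliably reconstructed afterwards.

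**What to change.** Add to section 4.a a de-identified screening and refusal log, kept from the first day of recruitment, with:

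- families eligible, approached and consented;
- route to the approach: census review, or referral by the committee or infectious disease;
- whether the child is a current or past vest user, or neither;
- any main reason for declining that the family volunteers, classed as vest-related or study-related.

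In the quantitative Data Analysis section, make uptake (consented over approached, with an exact 95% interval, also shown by route) part of Aim 1. Report it beside wear among enrolled families. State in advance that the feasibility conclusion will be limited to consenting families if uptake is low.

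The change needs no extra patients or visits. It costs a few minutes per approach. It also means holding minimal de-identified data on non-participants, which the data-handling text does not now cover and would need to. The feasibility figure may turn out less favourable.

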## Form A

IRB #	STU 2022-0306
-------	---------------

interviews which typically requires at least 8 interviews (Namey et al., 2016). Interviews will be open-ended questions lasting 15 to 45 minutes long utilizing an interview guide for consistency of interviewing. Probes may be utilized such as, "Can you tell me more about that?". Following each interview, recordings will be transcribed verbatim.

Every thirty days for 3 months parent satisfaction and feasibility of the protective wearable device will be collected using a quantitative survey. Patients may be approached within ambulatory clinic visits, inpatient visits, or by telephone. Study team will have a plus or minus seven-day timeframe around the 30-day window to collect the data. If the caregiver is present, then the caregiver will complete the survey on a Children's issued iPad via Microsoft Forms. If for some reason, the iPad is not working, which would be a rare occurrence, the caregiver will fill out a paper survey. Additionally, the electronic medical chart will be audited for any CVC complications such as line dislodgement, breaks, contamination, or CLABSI. At the end of the study data will be analyzed and collated.

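### The monthly parent surveys are not tied to whether the child still has a CVC, so a change in reported wear or satisfaction could not be separated from catheter loss

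*Combined protocol and SAP*

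**What the plan says.** The catheter requirement appears once, in section 4.a under Inclusion Criteria: "Patients with CVCs ages 0 to 12 years of age". No expected dwell time is attached to it.

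The schedule is the same for every family. Section 3 (Study Design) gives the scheme as "Every month complete 30-day satisfaction survey for a total of three data collection period-Discharge from study". Section 4.a repeats it as "Every thirty days for 3 months parent satisfaction and feasibility of the protective wearable device will be collected using a quantitative survey", with this window: "Study team will have a plus or minus seven-day timeframe around the 30-day window to collect the data".

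The same paragraph of 4.a says that the medical chart will be audited for CVC complications and gives dislodgement, breaks, contamination and CLABSI as examples. It gives no audit interval and does not mention planned removal.

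The quantitative Data Analysis paragraph of 4.a defines the wear measure: "Frequencies of nurse and caregiver reporting completion of the patient wearing the protective device will be calculated to evaluate feasibility and fidelity". It states no denominator. Parent satisfaction goes into a repeated measures ANOVA with descriptive statistics, and no rule covers removed catheters or missing surveys.

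One reason for stopping the vest is foreseen, under Exclusion Criteria: "If the patient does develop breast during the time of the study, then the patient will no longer wear the wrap". No rule says what happens to that family's remaining surveys.

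**The concern.** The vest exists to protect a catheter. Once the catheter is out, not wearing the vest is appropriate and says nothing about whether the vest is practical. If that non-wear enters the wear frequencies, it counts against feasibility, which is Aim 1. A satisfaction score given after removal is a recollection of past use, not a report on the preceding month.

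Catheter loss without replacement can only accumulate over the three surveys. It would therefore show as a trend in one direction even if wear among children with a CVC never changed. This differs from a family abandoning the vest or failing to respond.

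The protocol gives reason to expect some loss. Its background states that "One in four CVCs fail before completing intended therapy in the pediatric population", and removal at the end of therapy would come on top of that. Recruitment also reaches beyond the roughly 40 TPN-dependent children to transplant, pulmonary, oncology, general pediatric and rehabilitation patients, whose dwell times may differ.

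**Working it through.** **Is there a link to CVC status anywhere?** The possible places, taken in turn:

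- Eligibility: a CVC is required at entry only.
- Follow-up: three surveys and then discharge, with no catheter-based end or pause.
- Chart audit: complications only, no stated interval, no connection to the survey analysis.
- Analysis: wear frequencies without a denominator, and an ANOVA without a rule for catheter removal.

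No link is stated. The survey forms are not in the documents, so their items cannot be checked.

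**Figures in the plan.** The sample size cannot be re-derived, because the plan gives no inputs for it: "Sampling will continue for up to 30 patients to meet minimum requirements for statistical analysis for feasibility and satisfaction data". It is used here only as the number of families, N = 30, which makes 3 × 30 = 90 scheduled surveys. The one-in-four figure has no time frame, so it is not used as a 90-day rate.

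**Illustration for wear.** Assumptions, none from the documents: a fraction L of children are without a CVC by day 90, at a constant rate of loss; true wear is 80% at every survey among children with a CVC; wear is 0 after removal; all 30 children are in the denominator.

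- Share with a CVC at day t: S(t) = (1 − L)^(t/90)
- Apparent wear: 0.80 × S(t)
- Surveys after loss: 30 × Σ[1 − S(t)] over days 30, 60 and 90

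For L = 25%, S = 0.75^(1/3), 0.75^(2/3), 0.75 = 0.909, 0.825, 0.750. Apparent wear is 0.727, 0.660, 0.600. Surveys after loss are 30 × (0.091 + 0.175 + 0.250) = 15.5.

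For L = 10%, S = 0.965, 0.932, 0.900. Apparent wear is 0.772, 0.746, 0.720. Surveys after loss are 30 × (0.035 + 0.068 + 0.100) = 6.1.

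| Assumed loss by day 90 | Apparent wear, days 30 / 60 / 90 | Surveys after loss, of 90 | Expected with CVC at day 90, of 30 |
|---|---|---|---|
| 5% | 79 / 77 / 76% | 3.0 | 28.5 |
| 10% | 77 / 75 / 72% | 6.1 | 27.0 |
| 25% | 73 / 66 / 60% | 15.5 | 22.5 |
| 40% | 67 / 57 / 48% | 25.4 | 18.0 |

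The apparent fall from day 30 to day 90 is 77.2 − 72.0 = 5.2 points at 10% loss and 72.7 − 60.0 = 12.7 points at 25% loss. With a CVC-in-place denominator, wear is 80% at each survey by construction.

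**Will a rule be needed at all?** The chance of at least one loss among 30 is 1 − (1 − L)^30, which is 1 − 0.95^30 = 79% at 5% loss and 1 − 0.90^30 = 96% at 10%.

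**Illustration for satisfaction.** A repeated measures ANOVA was simulated with 30 families, 4,000 runs per setting, mean 4, SD 0.8, correlation 0.6 between surveys, every family answering, no true change while a CVC is in place, and a lower score after loss. All of these are assumptions. The time test at the 5% level rejects in about 5% of runs with no loss, and otherwise as follows:

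| Assumed loss by day 90 | Score 0.5 lower after loss | Score 1 lower after loss |
|---|---|---|
| 10% | 5% | 7% |
| 25% | 8% | 15% |
| 40% | 11% | 27% |

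**The case against.** The strongest reply is that the documents leave a gap but prescribe no error. Its parts:

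- **Who is surveyed.** Section 3 describes the respondents as parents of children using the vest. A child with neither line nor vest is arguably outside that group, and the flow scheme does not rule out earlier discharge. This stands as a possible reading, but no rule puts it into effect.
- **How non-wear is counted.** A reader might infer that catheter loss will be counted as non-wear. The documents do not say so. The denominator is unspecified rather than wrong, and a CVC-status item or a not-applicable option on the unseen forms cannot be excluded. This stands.
- **The one-in-four figure.** A reader might take it as the share without a line by day 90. It covers failure over intended therapy, with no 90-day frame. A failed line may also be repaired or replaced, and then the child still has a CVC. This stands, and it is why the working shows a range.
- **Satisfaction.** Nothing in the documents suggests that parents would score the vest lower because the line came out. At 10% loss the simulated rejection rate is 5% to 7%, close to nominal. This stands.
- **Aim 1.** Section 3 names the parent interview, at two weeks from recruitment, as the feasibility measurement. Even at 25% loss by day 90, only 1 − 0.75^(14/90) = 4% would have lost the line by day 14. No wear threshold or go/no-go rule is stated. This limits the consequence, but section 4.a also uses the monthly surveys and the wear frequencies for feasibility.
- **The chart audit.** It would catch some dislodgements and breaks. Planned removal is not listed, and the audit results are not tied to the survey analysis.

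Families without a line may also simply skip later surveys. A complete-case ANOVA would then drop them, about 30 × 0.25 = 7.5 families at 25% loss. That is selection instead of dilution, and it too needs a rule.

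**Conclusion.** The gap is real and moderate. The plan does not record CVC status at each survey and does not tie wear or satisfaction to time with a CVC. A decline in wear, or a shift in satisfaction, between months 1 and 3 could not be separated from catheter loss.

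The size cannot be fixed from the documents. Under the stated assumptions (80% true wear, none after removal, all 30 children counted), the spurious fall in wear is about 5 points at 10% loss and about 13 points at 25%. The satisfaction test is barely affected at 10% loss. It is materially affected only when both the loss and the post-removal score drop are large.

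The documents do not support the stronger conclusion that feasibility will be understated or that satisfaction will appear to fall. The point is that the data as planned could not show whether either had happened. The point does not reach the nurse satisfaction t-test.

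**What to change.** 1. At each monthly survey, within the existing window, record from the chart or the caregiver whether a CVC was in place during the prior 30 days, and the date and reason for any removal. A separate survey at the moment of removal is not needed, and it could fall outside the window: a removal on day 20 precedes the first window, which is days 23 to 37.
2. Calculate caregiver-reported wear over survey periods with a CVC in place. State in advance how a period with removal partway through is counted, and that a replaced line counts as in place. Report removals separately, as a count by reason.
3. Flag satisfaction scores given after removal. Analyse monthly satisfaction on CVC-in-place periods with a linear mixed model in place of the repeated measures ANOVA, so that families with one or two such surveys are kept. List the flagged scores descriptively.
4. State what happens to the remaining surveys of any family whose child stops the vest for another reason that the protocol names.

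The cost is one added data field, with its date and reason, and a wording amendment. There will be fewer analysable surveys at months 2 and 3, and the results will apply only while a CVC is in place. If removals are not captured during the study, this separation cannot be made reliably afterwards.
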